5.2 Eliciting and Reporting Adverse Events

The investigator will periodically assess subjects for the occurrence of AEs. To avoid bias in eliciting AEs, subjects should be asked the non-leading question: "How have you felt since yesterday/last time we spoke?" All AEs (serious and nonserious) reported by the subject must be recorded on the source documents and eCRFs provided by INC Research. Serious AE collection is to begin after a subject has signed the ICF/assent.

Use medical terminology in AE reporting. Adverse events should be reported as a single unifying diagnosis whenever possible or, in the absence of a unifying diagnosis, as individual signs or symptoms. Exacerbation or disease progression should be reported as

an AE only if there are unusual or severe clinical features that were not present, or experienced earlier, or not expected based on the course of the condition.

In addition, INC Research must be notified immediately by telephone or fax of any Immediately Reported Events (IREs) according to the procedure outlined below in [Section 5.3](#). Special attention should be paid to recording hospitalization and concomitant medications.

5.3 Immediately Reportable Events

The investigator must immediately report within 24 hours after either the investigator or site personnel become aware of any SAE, DILI, or confirmed pregnancy, by telephone or by fax to INC Research as outlined in [Appendix 1](#). An IRE form must be completed and sent by fax or overnight courier to INC Research. (Please note that the IRE form is NOT the AE eCRF.)

Subjects experiencing SAEs should be followed clinically until their health has returned to baseline status, or until all parameters have returned to normal, or have otherwise been explained. It is expected that the investigator will provide or arrange appropriate supportive care for the subject, and will provide prompt updates on the subject's status to INC Research.

5.3.1 Hyponatremia-related Adverse Events

5.3.1.1 Rapid Correction of Serum Sodium

When tolvaptan is not administered with adequate fluid intake, overly rapid correction of serum sodium may occur. Rapid correction of serum sodium level may lead to osmotic demyelination syndrome, a condition that can lead to severe brain damage and even death. Age-appropriate neurological examinations will be performed during administration of tolvaptan to monitor changes in health status in addition to serum sodium. This protocol is designed to provide adequate vigilance during the administration of tolvaptan to ensure that overly rapid correction does not occur in this pediatric population.

Rapid correction of hyponatremia is defined as any increase in serum sodium ≥ 12 mEq/L (mmol/L)/24 hours. If this change is observed during the trial, it should be reported as an IRE following the instructions detailed in [Section 5.3](#).

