	
Enrollment in this trial should follow completion or discontinuation of the previous tolvaptan hyponatremia trial. The subject must have been off investigational medicinal product (IMP) for at least 7 days between trials. A longer lapse between completion of the previous tolvaptan hyponatremia trial and enrollment into this trial is permitted while enrollment is open.
 
Subjects who consent/assent to participate will be followed once a month for 6 months, through telephone calls and/or clinical trial site visits. Subjects will attend the clinic for the baseline visit and a Month 6/end of trial visit. The remainder of the assessments will be conducted through telephone calls.
 
Optional Tolvaptan Treatment Component Subjects enrolled in the core safety follow-up component may be eligible for optional tolvaptan treatment. Tolvaptan treatment may be short-term treatment (eg, a few days of treatment needed per episode of hyponatremia) or long-term treatment (eg, treatment for weeks to months). The need for treatment for more than 30 days will be assessed by the investigator on a case-by-case basis.
 
Eligible subjects can be treated with tolvaptan at any time during the 6-month core safety follow-up component.
 
Treatment can be discontinued and reinitiated depending upon the individual subject's need (eg, during chemotherapy treatments). If subjects are off tolvaptan treatment for ≥ 72 hours, reinitiation of treatment (a new treatment cycle) will require reassessment of the eligibility criteria and will begin in a hospital setting. Tolvaptan should be titrated with regular serum sodium assessments.

Subject Population:
	
Approximately 100 male or female subjects will be enrolled in this trial. Eligible subjects will need to have participated in a previous tolvaptan pediatric trial for dilutional (euvoletic or hypervolemic) hyponatremia.

Inclusion/Exclusion Criteria:
	
Key inclusion criteria:
 
 • Enrollment in one of the previous tolvaptan pediatric trials for hyponatremia. • Willingness to be clinically followed for 6 months. 
Exclusion criteria:
 
 • There are no exclusion criteria for entry into the core safety follow-up component of this trial.

	The optional tolvaptan treatment component has additional eligibility criteria.
Trial Sites:	Subjects may be enrolled at approximately 75 clinical trial sites globally.

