3.7.2 Optional Tolvaptan Treatment Component

If a subject has a clinical need for tolvaptan, the subject may be screened for eligibility to be treated with tolvaptan (see [Appendix 5](#)). To assess the subject's eligibility to receive tolvaptan, the subject must have been off treatment with IMP for 7 days following the end of treatment in the previous tolvaptan trial.

Subjects who meet the eligibility criteria for tolvaptan treatment will be administered tolvaptan based on age, weight, and the use of CYP3A4 inhibitors on Day 1 of the cycle. Subsequent dosing adjustments are based on serum sodium response. Refer to [Section 3.2.1.2](#) for dosing guidelines.

Trial assessments and time points for the optional tolvaptan treatment component are summarized in [Table 3.7.2-1](#) and described in [Section 3.7.3.2](#).

Table 3.7.2-1 Schedule of Assessments for Each Treatment Cycle																	
Procedures^a	Pre-treatment Baseline^b	Titration Phase^b			Post-titration						Treatment Cycle Month 2	Treatment Cycle Month 3+ (Maintenance)	Month 6 (D173) Cycle DC (+ 2 wk)	Follow-up Phase^k			
		Day 1	Day 2 and 3	Day 4	Day 7, 14 and 21	Day 30 (±1)	Day 31^c	Day 32^c	Day 33^c	Day 34^c				24 (±4) hours post-last dose	7 (±1) days post-last dose	14 (±2) days post-last dose	
	Days -4 to -1										every 2 weeks (±2 days) Mth 2 Wk 2 (D47), Mth 2 Wk 4 (D61)	Once monthly (±2 days) Mth 3 (D89), Mth 4 (D117), Mth 5 (D145)					
Review eligibility criteria for treatment	X																
Vital signs	X	X	X	X	X	X	X	X	X	X	X	X	X	X	X	X	
Physical examination ^d	X											X	X				
Body height and weight/ growth percentiles	X											X	X				
Pregnancy test ^e	X								X		X	X		X			
Clinical status assessment	X						X	X	X	X	X	X					
Neurological assessment ^f	X						X	X	X	X	X	X					
Quality of Life assessment	X											X					
Assess ALT, AST, BT, and creatinine	X					X					X ^g	X	X	X			
Assess serum sodium ^h	X	X	X	X	X	X	X	X	X	X	X	X	X	X	X	X	

- ^bTitration can be up to 4 days. Cycles can be repeated as needed during the 6-month core safety component. If a subject is off tolvaptan treatment for ≥ 72 hours, titration/reinitiation of tolvaptan will require reassessment of eligibility criteria and will begin in a hospital setting as part of a new treatment cycle.
- ^cDuring the Day 30 treatment interruption, Days 31, 32, 33 and 34 must follow consecutively. Once the Day 30 visit is determined, the subsequent visit days do not have a window.

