- 3) In addition to serum sodium samples obtained for treatment qualification and efficacy endpoints, supplemental samples for the purposes of safety assessment only will be obtained using a POC sodium assessment unit, where available, on Day 1 at 4 to 6 (+0.25) hours postdose and at 18 (\pm 1) hours postdose. A POC assessment unit is preferred; however, regular blood draws may be used (especially if they can be combined with standard of care labs).
- 4) Tolvaptan will be administered.

- 5) A blood sample for serum sodium testing will be collected 8 (-1 to +0.25) hours post-first dose.
- 6) Concomitant medications will be recorded.
- 7) Adverse events will be assessed.

[Table 3.7.4.1.2-1](#) presents the efficacy and safety serum sodium samples required during Day 1 of the titration period.

3.7.3.2.2 Day 2 up to Day 4

The investigator should schedule evaluations daily while the subject remains in a hospital setting per the schedule of assessments. The following procedures will be performed during the titration period:

- 1) Vital signs (blood pressure, heart rate, respiratory rate, and temperature) will be assessed after the subject has been supine for ≥ 3 minutes. Vital signs should be assessed prior to blood draws.
- 2) A blood sample for serum sodium testing must be assessed at 24 (± 4) hours post-dose (trough) on Days 2, 3, and 4. The results must be reviewed prior to tolvaptan dosing.
- 3) In addition to serum sodium samples obtained for treatment qualification and efficacy endpoints, supplemental samples for the purposes of safety assessment will be obtained using a POC sodium assessment unit, where available, at 6 (-1 to +0.25) hours postdose and at 18 (± 1) hours postdose on Days 2, 3, and 4 during the titration period. A POC assessment unit is preferred; however, regular blood draws may be used (especially if they can be combined with standard of care labs).
- 4) Administer tolvaptan. Tolvaptan will be titrated per the titration guidelines (see [Section 3.2.1.2](#)).
- 4) On Day 4, if a stable dose of tolvaptan has been confirmed, the initial titration phase will conclude, and sufficient tolvaptan will be dispensed for subjects that are outpatients for QD dosing until their next scheduled visit. Subjects and their parents/legal guardians will be instructed to return any remaining tolvaptan at the next visit for dose reconciliation.
- 6) Concomitant medications will be recorded.
- 7) Adverse events will be assessed.

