3.7.3.2.4 Day 30 Interruption: 30 (± 1) Days Post-first Dose

After 30 days of tolvaptan treatment, all subjects (exceptions explained in [Section 3.1.2.1](#)) should discontinue treatment for up to 2 doses to assess the continued need for tolvaptan treatment. Subjects should arrive to the clinic prior to taking the morning dose of tolvaptan.

The following assessments will be performed during the Day 30 visit:

- 1) Vital signs (blood pressure, heart rate, respiratory rate, and temperature) will be assessed after the subject has been supine for ≥ 3 minutes. Vital signs should be assessed prior to blood draws.
- 2) A blood sample for serum sodium testing must be assessed at 24 (± 4) hours post-last dose with the results reviewed prior to subsequent tolvaptan dosing.
- 3) A blood sample for ALT, AST, BT, and creatinine will be collected.
- 4) Tolvaptan dispensed the previous week will be returned for accountability.
- 5) Tolvaptan will be administered during the clinic visit.
- 6) Concomitant medications will be recorded.
- 7) Adverse events will be assessed.

- 8) Instruct subjects to return to the clinic for visits on Day 31 and 32.

3.7.3.2.4.1 Day 31

The following assessments will be performed:

- 1) Vital signs (blood pressure, heart rate, respiratory rate, and temperature) will be assessed after the subject has been supine for ≥ 3 minutes. Vital signs should be assessed prior to blood draws.
- 2) A clinical status assessment will be performed. If the subject has any positive findings on the clinical status assessment, a full neurological examination can be performed per investigator judgment.
- 3) A blood sample will be collected for serum sodium testing at 24 hours (± 4 hours) post the Day 30 dose. Refer to [Figure 3.1-1](#) for a trial schematic, and [Section 3.2.1](#) for a description of the treatment continuation decision.
- 4) Concomitant medications will be recorded.
- 5) Adverse events will be assessed.

3.7.3.2.4.2 Day 32

The following assessments will be performed:

- 1) Vital signs (blood pressure, heart rate, respiratory rate, and temperature) will be assessed after the subject has been supine for ≥ 3 minutes. Vital signs should be assessed prior to blood draws.
- 2) A clinical status assessment will be performed. If the subject has any positive findings on the clinical status assessment, a full neurological examination can be performed per investigator judgment.

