3.7.5.8 Clinical Status Assessment

Clinical status assessments will be performed per inpatient standard of care and should include review of patient chart entries, including hyponatremia assessment notes, trial- and nontrial-specific laboratory results, any examination findings, medical problem list changes, and fluid intake and output to evaluate overall subject eligibility in terms of hyponatremia state. The clinical assessment will focus on symptoms and signs which will inform treatment decisions (eg, the need to switch to rescue therapy, or the ability to safely discharge a subject from the hospital). The clinical assessment should be performed by a trial investigator who will be aware of laboratory and other clinical response data.

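### Neurological examinations are promised during tolvaptan administration, but no neurological or clinical status assessment is scheduled from Day 1 to Day 30 or in a cycle's Follow-up Phase

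*Protocol*

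**What the plan says.** Section 5.3.1.1 warns that rapid correction can cause osmotic demyelination, with possible severe brain damage or death. It then commits to an examination: "Age-appropriate neurological examinations will be performed during administration of tolvaptan to monitor changes in health status in addition to serum sodium".

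Section 3.7.5.8 describes the clinical status assessment as inpatient in character, including a review of fluid intake and output. It gives as examples of the decisions informed "the need to switch to rescue therapy, or the ability to safely discharge a subject from the hospital".

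Table 3.7.2-1 has one row for each, "Neurological assessment" and "Clinical status assessment". After the first pretreatment baseline, a full neurological examination is optional and depends on the other row. The Day 31 list reads: "If the subject has any positive findings on the clinical status assessment, a full neurological examination can be performed per investigator judgment".

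Section 3.7.3.2.2 requires initiation and titration in hospital. For Days 2 to 4 it says: "The investigator should schedule evaluations daily while the subject remains in a hospital setting per the schedule of assessments". It continues: "On Day 4, if a stable dose of tolvaptan has been confirmed, the initial titration phase will conclude", after which drug is dispensed to outpatients.

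The synopsis gives as an example of short-term use "a few days of treatment needed per episode of hyponatremia".

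**The concern.** Sodium sampling detects over-correction. The neurological examination looks for its effect on the child. Section 5.3.1.1 presents the second as an addition to the first, so a reader expects to find it in the schedule while the dose is being started and adjusted. It is not there, and neither is the clinical status assessment that is meant to support rescue and discharge decisions.

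Two things are at stake. A site that follows the table will not perform a safeguard the text says will be performed. And for a short cycle, an absence of neurological findings could not be read as a negative examination, because no examination was due between the first dose and the end of that cycle's follow-up.

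**Working it through.** No sample size or error rate is involved. The check sets the promise beside the schedule.

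**Step 1: read Table 3.7.2-1 by column.** As a check on the reading, the pregnancy-test row read the same way falls on pretreatment, Day 33, Month 2, Month 3+ and the 24-hour follow-up. That matches the visit lists.

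| Contact | Neurological and clinical status rows | Physical examination row |
|---|---|---|
| Pretreatment baseline | marked | marked |
| Days 1, 2, 3, 4 (titration) | blank | blank |
| Days 7, 14, 21 | blank | blank |
| Day 30 | blank | blank |
| Days 31, 32, 33, 34 | marked | blank |
| Month 2 | marked | blank |
| Month 3+ | marked | marked |
| Month 6 (D173)/Cycle DC | blank | marked |
| 24 hours, 7 days, 14 days after last dose | blank | blank |

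**Step 2: count.**
- Day 1 to Day 30: 4 + 3 + 1 = 8 treatment days, 0 of 8 marked.
- Follow-up Phase: 3 contacts (two visits and one telephone call), 0 of 3 marked.
- Days 31 to 34: 4 of 4 marked.

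**Step 3: compare with the visit lists.** Sections 3.7.3.2.2 (Days 1 to 4), 3.7.3.2.3 (Days 7, 14, 21), the Day 30 list in 3.7.3.2.4, and 3.7.3.2.7 (follow-up) contain neither item. Day 31 is the first that does, and it falls when the first dose is withheld. Table and text agree, so this is not a slip in one of them.

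**Step 4: look for another route to an examination on Days 1 to 30.**
- Section 3.7.5.5 makes a neurological examination part of each directed physical, but the physical examination row is blank on these days too.
- The optional full examination is triggered by a positive clinical status assessment, and that trigger is itself unscheduled here.
- The daily evaluations on Days 2 to 4 are tied to the schedule of assessments, which returns the reader to the blank cells.
- Section 3.7.5.1 requires monitoring for neurologic symptoms without naming an examination or time, and refers to Section 5.3.1, where the unscheduled promise sits.

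**Step 5: follow a child treated for a few days.** Footnote k and the end of Section 3.7.3.2.6.1 send the child to the Follow-up Phase, where neither assessment is listed. The next scheduled neurological examination is then the one inside the directed physical at core Month 6/early termination (Sections 3.7.3.1.3, 3.7.5.4 and 3.7.5.5). That may be up to about 6 months later, depending on when treatment began. If a new cycle starts first, its pretreatment baseline (Section 3.7.3.2.1) brings a clinical status assessment and a physical examination sooner.

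**The case against.** The strongest reply is that the early days are closely watched by other means. Titration is in hospital. Table 3.7.4.1.2-1 samples sodium several times on each of Days 1 to 4, and Sections 3.2.1.2 and 3.8.3 set actions on the results. Section 3.7.5.1 requires active monitoring for symptoms suggesting demyelination and for signs of dehydration, and Section 5.3.1.2 asks for close monitoring of the same events. Adverse events are assessed at every visit and elicited by question (Section 5.2). Section 3.7.5 leaves safety monitoring frequency to the investigator. All of this stands. It rules out any inference that detection would depend on spontaneous reports, or that neurological examination is the main safeguard. It does not supply the examination that Section 5.3.1.1 says will take place, and discretion is weaker than that commitment.

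It can also be said that Section 5.3.1.1 gives no time points, and that Month 2 and Month 3+ assessments are during administration. That is fair for long cycles. For a cycle ending by Day 30, nothing in the schedule meets the sentence.

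A reader might infer that a briefly treated child is never examined after the first dose. The documents do not support this: the core Month 6/early termination visit includes a directed physical with a neurological examination, and a repeat cycle begins with a new baseline. A reader might also point to children who cannot report symptoms. The protocol's remark on limited communication concerns thirst, especially in infants. Appendix 5 restricts treatment to age 4 years and over, and Section 3.3.2 requires closer observation, or ineligibility, where the ability to sense or communicate thirst is impaired.

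Finally, neurological examination is not an endpoint, and Section 7.6.3 only lists physical examination data. The consequence is for safety interpretation, not for a planned analysis.

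**Conclusion.** The contradiction holds and is specific. A named safeguard against a potentially fatal harm is scheduled at 0 of 8 treatment days from Day 1 to Day 30 and 0 of 3 Follow-up Phase contacts. The assessment said to inform rescue and discharge is absent from the whole titration stay. For a few days' treatment, the next scheduled neurological examination may be the core Month 6/early termination visit.

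This rests on two readings. The core visit content is taken from Sections 3.7.3.1.3 and 3.7.5.4. The Month 6/Cycle DC column is taken to apply at Month 6, because footnote k routes earlier stoppers to the Follow-up Phase. If that column meant any cycle discontinuation, its physical examination would narrow the gap for short cycles but would not fill Days 1 to 30 of treatment.

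SAP Sections 5.1 and 5.2 record that no subject received optional tolvaptan. The gap therefore affected no treated child here, and the point is about the plan as written and any protocol that reuses this schedule.

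**What to change.** Reconcile Table 3.7.2-1 and Sections 3.7.3.2.2 to 3.7.3.2.4 and 3.7.3.2.7 with Sections 5.3.1.1, 3.7.5.5 and 3.7.5.8, so that the schedule delivers the examinations the text says will be performed. The two assessment rows already exist and can be used at contacts that already take place. Which visits carry them is for the sponsor to decide. The optional full examination after a positive finding can stay as it is.

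The cost is slightly longer visits and extra form entries. No new visit or blood sample is needed.

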5.3.1.2 Other Hyponatremia-related Adverse Events

Other events related to hyponatremia should be monitored closely and reported as appropriate depending on their severity:

- Absolute serum sodium level ≥ 145 mEq/L
- Any increase in serum sodium > 8 mEq/L [mmol/L] over a 10-hour period
- Neurological symptoms or other signs or symptoms suggestive of osmotic demyelination
- Worsening symptoms of hyponatremia
- Hypovolemia or hypotension requiring intervention
- Signs and symptoms of dehydration

All AEs must be monitored until symptom resolution or until the condition stabilizes.

5.4 Potential Drug-induced Liver Injury

For a subject who experiences an elevation in AST or ALT that is $\geq 2 \times$ ULN or whose levels increase ≥ 2 times their initial baseline value, a BT level should also be evaluated. Elevated values should be confirmed via retest. If the BT is $\geq 2 \times$ ULN or ≥ 2 times their baseline value, an IRE form should be completed with all values listed and also should be reported as an AE on the eCRFs.

If hepatic injury is suspected, tolvaptan should be promptly discontinued, appropriate treatment should be instituted, and investigations should be performed to determine probable cause. Such an event should be reported and followed until resolution.

5.4.1 Liver Transaminase Elevations

Management of abnormal liver function test results should be based on the investigator's clinical judgment. A liver function test result that is $2 \times$ ULN is generally accepted as a medically significant occurrence across various medical disciplines.

For a subject that experiences an elevation in AST or ALT that is $\geq 2 \times$ ULN or whose levels increase ≥ 2 times their initial baseline value in subjects with an elevated baseline value, a BT level should also be evaluated. If the BT is $\geq 2 \times$ ULN or ≥ 2 times their baseline value in subjects with an elevated baseline value, an IRE form with all values listed should be completed and also reported as an AE on the eCRFs.

The following guideline for repeat testing may be used by investigators as a reference for any subject with an ALT or AST $\geq 2 \times$ ULN:

- 1) ALT, AST, alkaline phosphatase, and BT should be repeated within 48 to 72 hours (needed to confirm abnormalities and determine if they are increasing or decreasing).
- 2) Inquiries should be made about symptoms (fatigue, nausea, vomiting, right upper quadrant pain or tenderness, fever, and/or rash) and signs like jaundice, yellowish discoloration of sclera, etc.
- 3) If discharged or transferred, the subjects should be retested locally and results given to the investigator immediately, along with that laboratory's normal ranges.
- 4) Close observation is required if symptoms persist or repeat testing shows ALT or AST $\geq 3 \times$ ULN for subjects with normal baseline measures OR 2-fold increases above baseline values for subjects with elevated values before drug exposure. If close monitoring is not possible, the drug should be interrupted until such monitoring is possible or the drug should be permanently discontinued.
- 5) All trial subjects with evidence of possible DILI should be followed until all abnormalities return to normal or to the baseline state.

Close observation may involve:

- 1) Repeating liver enzymes and serum bilirubin tests 2 or 3 times weekly.
- 2) Frequency of retesting can decrease to once a week or less if abnormalities stabilize or if the trial drug has been interrupted/discontinued and the subject is asymptomatic.
- 3) Obtaining a more detailed history of symptoms and prior or concurrent diseases.
- 4) Obtaining a history of concomitant drug use (including non-prescription medications and herbal and dietary supplement preparations), alcohol use, recreational drug use, special diets, and change in diet.
- 5) Ruling out acute viral hepatitis types A, B, C, D, and E; autoimmune or alcoholic hepatitis, nonalcoholic steatohepatitis; hypoxic/ischemic hepatopathy; and biliary tract disease.
- 6) Obtaining a history of exposure to environmental chemical agents.
- 7) Obtaining additional tests to evaluate liver function, as appropriate (eg, international normalized ratio [INR], direct bilirubin).
- 8) Considering gastroenterology or hepatology consultations.

5.4.1.1 Criteria for Discontinuation from the Optional Tolvaptan Treatment Component of the Trial due to Liver Transaminase Elevations

A subject must be discontinued from tolvaptan treatment on confirmation of any of the following criteria:

- 1) ALT or AST $\geq 8 \times$ ULN
- 2) ALT or AST $\geq 5 \times$ ULN for more than 2 weeks
- 3) ALT or AST $\geq 3 \times$ ULN AND (BT $\geq 2 \times$ ULN or INR > 1.5)
- 4) ALT or AST $\geq 3 \times$ ULN with appearance of fatigue, nausea, vomiting, right upper quadrant pain or tenderness, fever, rash, and/or eosinophilia ($> 5\%$) and signs of jaundice

If there is any question about how to proceed with a particular subject's case, do not hesitate to contact your regional medical monitor to discuss treatment options. The FDA has issued a guidance for industry regarding this topic. This guidance is not specific to hyponatremia. Otsuka is integrating many of the recommendations in this guidance into all of its clinical research programs. Links to this guidance and information from the FDA regarding drug-induced liver injury are provided in the references.^{25,26}

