3.7.5.1 Adverse Events

Refer to [Section 5](#), Reporting of Adverse Events.

In addition, for subjects on tolvaptan treatment, active monitoring is required for:

- Absolute serum sodium level ≥ 145 mEq/L (mmol/L)
- An overly rapid correction of the serum sodium level (an increase in serum sodium of > 8 mEq/L [mEq/L (mmol/L)] over a 10-hour period, ≥ 12 mEq/L [mEq/L (mmol/L)] over a 24-hour period, or a rate of correction in serum sodium concentration that the investigator deems too rapid)
- Neurologic symptoms, or other signs or symptoms suggestive of osmotic demyelination (see [Section 5.3.1](#) for more details)
- Elevations in AST or ALT that are $\geq 2 \times$ ULN or levels that increase ≥ 2 times their previously observed level. If this occurs, a BT level should also be

evaluated. See [Section 3.7.5.3.1](#) for more information and [Section 5.4](#) for detailed instructions on how this type of event should be captured

- Worsening symptoms of hyponatremia
- Hypovolemia or hypotension requiring intervention.
- Clinical signs and symptoms of dehydration

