3.8.3 Individual Subject Discontinuation

If a subject discontinues from the trial prematurely, the reason must be fully evaluated and recorded appropriately in source documents and the eCRF. If the subject is being withdrawn because of an AE, that AE should be indicated as the reason for withdrawal.

All subjects have the right to withdraw at any point during the trial without prejudice. The investigator can discontinue a subject's participation in the trial at any time if medically necessary. In addition, subjects meeting the following criteria must be withdrawn from tolvaptan treatment:

- a) Occurrence of any AE, intercurrent illness, or abnormality in a laboratory assessment which, in the opinion of the investigator, warrants the subject's permanent withdrawal of tolvaptan treatment;
- b) Treatment with a prohibited concomitant medication other than the use of appropriate medications for the treatment of AEs under direction of the investigator;
- c) Subject noncompliance, defined as refusal or inability to adhere to the trial schedule or procedures (see [Section 3.12](#), Subject Compliance);
- d) At the request of the subject, investigator, Otsuka Pharmaceutical Development & Commercialization, Inc. (OPDC) or designee, or regulatory authority;
- e) Subject becomes pregnant; or
- f) Subject is lost to follow-up.

In addition, subjects on tolvaptan treatment who meet the following criteria should have results confirmed with a repeat test. Sodium tests should be done either STAT or through bedside monitoring.

- The subject's serum sodium increases by > 8 mEq/L (mmol/L) in any 10-hour period following dosing on Day 1 of a cycle
- The subject's serum sodium increases by ≥ 12 mEq/L (mmol/L) in the 24-hour period following dosing
- At any time after dosing, the subject's serum sodium is ≥ 145 mEq/L (mmol/L).
- Evidence of dehydration
- Abnormal liver function tests (see [Section 5.4](#))

If the result is confirmed, the medical monitor should be contacted to consider options of down-titration, dose discontinuation, concomitant medication adjustment, fluid supplementation, and/or withdrawal.

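### Two mandatory liver stopping rules (INR above 1.5; at least 5 × ULN for over two weeks) depend on measurements that Protocol Section 5.4.1 does not require

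*Protocol*

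**What the plan says.** Section 5.4.1.1 is worded as an obligation: "A subject must be discontinued from tolvaptan treatment on confirmation of any of the following criteria". Criterion 2 applies to ALT or AST at or above 5 × "ULN for more than 2 weeks". Criterion 3 applies at 3 × ULN or more together with either bilirubin of at least 2 × ULN or INR above 1.5.

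The monitoring meant to feed these rules is in Section 5.4.1 and is permissive. The repeat-testing list is offered as a reference that investigators may use. Its first item is a repeat of ALT, AST, alkaline phosphatase and bilirubin at 48 to 72 hours. Item 4 starts close observation at 3 × ULN for children with normal baselines, and for raised baselines at "2-fold increases above baseline values for subjects with elevated values before drug exposure". Persisting symptoms also start it. Close observation in turn may involve enzyme and bilirubin tests two or three times a week, falling to weekly or less if values stabilize. It may also involve "Obtaining additional tests to evaluate liver function, as appropriate (eg, international normalized ratio [INR], direct bilirubin".

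Outside that section, Table 3.7.5.3-1 and Appendix 6 list the laboratory tests on treatment. The liver tests are ALT, AST and bilirubin. INR is in neither. Appendix 5, ineligibility item 17, excludes only liver values above 3 × ULN, so a child at 3 × ULN may be treated.

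**The concern.** A stopping rule that must be obeyed works only if the value it depends on is measured in time. Here the obligation sits in one section, and the measurement is left optional in another. An INR above 1.5 could go unseen because nobody was required to draw it. A child at or above 5 × ULN could stay on drug beyond two weeks because the next required panel comes about a month later.

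Raised baselines are foreseeable, because Section 3.3.2 names hepatocellular disease, including cirrhosis, among the conditions to be treated (although severe liver disease is ineligible). The protocol itself treats liver injury as a recognized tolvaptan risk: Section 1.3 describes the transaminase imbalance and three cases meeting Hy's Law laboratory criteria in the adult polycystic kidney programme.

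**Working it through.** The plan gives no figure of its own on this point, so there is nothing to reproduce. The check compares thresholds and test dates.

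**Inputs**
- Baseline ALT or AST, written as b × ULN: treatable up to b = 3 (Appendix 5, item 17).
- Close-observation trigger: 3 × ULN for a normal baseline, 2b × ULN for a raised one (5.4.1, item 4).
- Stopping thresholds: 5 × ULN for more than 14 days (criterion 2); 3 × ULN with INR above 1.5 (criterion 3).
- On-treatment liver panels: Day 30 ± 1 (3.7.3.2.4); Day 61 ± 2, with none at the Day 47 visit (3.7.3.2.5); Days 89, 117, 145 and 173, each ± 2 (3.7.3.2.6.1).

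**Step 1: is an INR ever required?**
- Table 3.7.5.3-1: no.
- Appendix 6: no.
- The 48 to 72 hour repeat: no.
- Close observation: only as an example, where appropriate, of what it may involve.

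So no INR is required for any child, at any baseline or enzyme level. The bilirubin limb of criterion 3 is supported, because bilirubin is in every scheduled panel and in the repeat.

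**Step 2: is the two-week duration ever checked on time?**
- Nominal gaps: 61 − 30 = 31 days; 89 − 61, 117 − 89, 145 − 117 and 173 − 145 are each 28 days.
- With windows, first gap: 59 − 31 = 28 to 63 − 29 = 34 days.
- With windows, later gaps: 28 − 4 = 24 to 28 + 4 = 32 days.
- Days past the 14-day point at the next scheduled panel: 28 − 14 = 14 to 31 − 14 = 17 nominally; 24 − 14 = 10 to 34 − 14 = 20 with windows.

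The confirmatory repeat falls two to three days after the first value, so it cannot show persistence beyond 14 days. The tests that could are the ones close observation may involve, and these are optional at every baseline.

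**Step 3: where does close observation start relative to 5 × ULN?**

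For a raised baseline the trigger is 2b. It exceeds 5 when b > 5/2 = 2.5.

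| Baseline b | Trigger 2b | Enzyme range at or above 5 but below the trigger |
|---|---|---|
| 2.5 | 5.0 | none |
| 2.6 | 5.2 | 5.0 to 5.2 |
| 2.8 | 5.6 | 5.0 to 5.6 |
| 3.0 | 6.0 | 5.0 to 6.0 |

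In that range an asymptomatic child does not even reach the point at which close observation begins. This takes the twofold wording to mean reaching 2b. If it meant a rise of twice the baseline, to 3b, the range would open at b > 5/3 = 1.67, so the reading used here is the narrower one.

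**Step 4: the other criteria**
- Criterion 1 (8 × ULN) has no duration element, and the largest trigger, 6 × ULN, lies below it.
- Criterion 4 has an eosinophilia limb, and no blood count is required either. That limb has the same status as INR.

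**The case against.** The best reply is that judgment is the declared design. Section 5.4.1 opens by basing management on the investigator's clinical judgment. Section 3.7.5 leaves the frequency of safety monitoring to the investigator, with protocol sampling as a minimum, and Section 5.1 makes the investigator responsible for reviewing every result. Monthly panels are therefore a floor. Several safeguards sit above it:
- Section 3.7.5.1: "for subjects on tolvaptan treatment, active monitoring is required for" enzyme elevations from 2 × ULN, among other events.
- Section 5.4: a retest, and "If hepatic injury is suspected, tolvaptan should be promptly discontinued".
- Section 3.8.3: "If the result is confirmed, the medical monitor should be contacted to consider options of" changing or stopping treatment.
- Section 5.4.1, item 4: "If close monitoring is not possible, the drug should be interrupted until such monitoring is possible or the drug should be permanently discontinued".

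The path to harm in the 2.5 to 3 × ULN group is also narrow. It needs a large rise that stays under twofold, no symptoms, persistence past two weeks, and no further test after a confirmed value at or above 5 × ULN. Leaving INR to discretion has some logic too, since a child with liver disease may have a raised INR before any drug.

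Much of this stands. In practice most investigators would retest a child at 5 × ULN. But none of these provisions names an INR or sets an interval within two weeks, and a rule worded as an obligation needs both.

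A reader might infer that the two rules cannot be applied at all. The documents do not support that: an INR can be ordered, and criterion 2 can be applied, late, at the next panel. A reader might also infer that the duration problem is confined to baselines above 2.5 × ULN and that lower baselines are protected. That is not supported either, because the tests under close observation are optional throughout. The 2.5 to 3 × ULN group is where the gap is plainest, and lower baselines share it.

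**Conclusion.** The concern holds as a minor design gap. The INR limb of criterion 3 has no required measurement in any child. Criterion 2 has no binding retest interval at any baseline. If nobody orders extra tests, it would be applied nominally 14 to 17 days late (10 to 20 with visit windows). For baselines above 2.5 and up to 3 × ULN, the close-observation trigger itself lies above the stopping threshold.

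The delay figures assume that an elevation is first seen at a scheduled panel, persists without symptoms, and is followed only by the confirmatory retest. They describe what the text permits and do not predict what sites would do. The documents give no count of children with raised baselines, so the size of the affected group is unknown.

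SAP Sections 5.1 and 5.2 report that no subject received optional tolvaptan. No child in this trial was exposed to the gap and no result depends on it.

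**What to change.** Amend Section 5.4.1 as follows.

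- **INR.** Require an INR with the 48 to 72 hour retest whenever ALT or AST is at least 3 × ULN. In children with raised ALT or AST, also obtain an INR at the pretreatment baseline. A child at exactly 3 × ULN already meets the enzyme part of criterion 3, so any pre-existing coagulopathy should be known before dosing.
- **Interval.** At any baseline, require liver panels at least weekly while ALT or AST is at or above 5 × ULN on drug.
- **Trigger.** For raised baselines, start close observation at the lower of 2 × baseline or 5 × ULN.

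Weekly panels add about three draws (days 7, 14 and 21) before criterion 2 is met or the value falls. The first result beyond day 14 is at day 21, so the delay shrinks to at most 21 − 14 = 7 days. The trigger changes only for b > 2.5 and still needs a rise of 5/3.0 − 1 = 67% at b = 3.0, or 5/2.6 − 1 = 92% at b = 2.6, so a stable child would not meet it. The first on-treatment INR comes from a sample already being drawn.

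The cost is protocol wording, a few extra blood tests, and possibly earlier interruption or stopping in a small subgroup. Where close monitoring is not possible, item 4's interruption rule would start at 5.0 × ULN, instead of 5.2 × ULN at b = 2.6 or 6.0 × ULN at b = 3.0. A child with liver disease and an INR already above 1.5 would meet criterion 3 once ALT or AST is at least 3 × ULN, and the baseline INR makes that visible before treatment starts.
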